6.1 Inclusion Criteria

Inclusion criteria for AIS patients:

- Selection of 182 patients with first-ever acute ischemic stroke (AIS) who are hospitalized at our hospital, aged ≥ 18 years, with no restriction on gender;
- Patients must be admitted within 24 hours of the onset of AIS;
- Diagnosis must be confirmed by cranial magnetic resonance imaging (MRI) or computed tomography (CT);
- All enrolled patients must provide written informed consent.

Inclusion criteria for healthy controls:

- Age and gender matched;
- No organic diseases;
- Written informed consent must be signed

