2.2 Research Background

Microglia, the primary immune cells in the brain, are among the first cells to activate after AIS, playing a critical role in accelerating inflammation, increasing or reducing neuronal apoptosis, and regulating the post-stroke inflammatory microenvironment, thus affecting stroke prognosis (*J Neuroinflammation*. 2022;19(1):88). KLK10, also known as normal epithelial cell-specific molecule-1, is one of the 15 secreted serine proteases in the kallikrein family. Previous studies have shown that KLK10 is expressed in endothelial cells, where it participates in regulating endothelial inflammation and atherosclerosis (*Elife*. 2022;11:e72579). Our recent systematic observations of KLK10's spatial-temporal expression and cellular distribution in the brain after ischemia revealed that this molecule is expressed not only in cerebral endothelial cells but also in microglia and astrocytes. While it did not significantly increase in

the ischemic penumbra in the early stages (2-4 days post-ischemia), it was highly expressed in the infarct core area at 2 days post-ischemia and significantly co-labeled with microglia. The specific high expression of KLK10 in microglia in specific brain regions post-AIS suggests that it may be involved in early pathological damage after cerebral ischemia. Given that the permeability of the blood-brain barrier (BBB) changes within 6 hours of stroke onset (*Front Neurol.* 2020;11:594672), and since KLK10 is a secreted molecule, it is likely that its expression can be detected in the blood of AIS patients. Whether plasma KLK10 levels can reflect changes in neuroinflammatory damage in AIS patients and serve as a specific biomarker for predicting AIS prognosis remains unclear and warrants further investigation.

TREM2 is an innate immune receptor in the brain, consisting of an extracellular immunoglobulin-like domain, a transmembrane domain, and a cytoplasmic portion. Post-stroke, TREM2 is activated by nucleotides, lipid mediators, and other key factors released by apoptotic neurons, cells/myelin debris, playing an important role in regulating neuronal damage (*Front Immunol.* 2019, 10: 1668). Literature shows that TREM2 molecules are mainly expressed in microglia and can reflect their activation status. Elevated plasma sTREM2 levels are closely associated with increased risk of death and cardiovascular events one year after AIS onset (*J Neuroinflammation.* 2022;19(1):88).

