5.1 Overall Design

A total of 182 patients with first-ever anterior circulation AIS (Acute Ischemic Stroke) hospitalized in the Neurology Department at the Northern Campus of our hospital will be selected as the observation group, and 91 healthy individuals undergoing physical examination will be selected as the control group. For AIS patients, 10 ml of elbow venous blood will be collected at admission and then at 24 hours and 7 days after stroke onset. For healthy individuals, 10 ml of fasting elbow venous blood will

be collected once. The dynamic changes and differential expression characteristics of a group of neuroinflammatory molecules, including KLK10, sTREM2, and GFAP in plasma will be observed. The early changes (at admission and 24 hours after onset) of these neuroinflammatory molecules in plasma will be compared and analyzed in relation to the severity of acute neurological deficits (NIHSS score), infarct volume, brain edema, hemorrhagic transformation, occurrence of progressive stroke, and clinical prognosis at 3 months (mRS score), to evaluate the predictive value of these molecules for clinical outcomes after AIS.

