6.3 Recruitment of research subjects

- Source of subjects: AIS patients will be recruited from inpatients in the Department of Neurology at the Northern Campus; healthy controls will be selected from outpatient health check-up populations who have undergone routine blood tests, biochemical tests, cranial CT, or MRI
- Recruitment site: Ruijin Hospital Northern Campus

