10.5 Baseline Descriptive Analysis

Descriptive statistics are used to compare demographic characteristics and laboratory indicators at baseline between groups. Continuous variables such as age, blood pressure, blood glucose levels, infarct volume, ASPECTS score, neurological function (NIHSS) score, and levels of neuroinflammatory molecules (KLK10, sTREM2, and GFAP) are expressed as mean (standard deviation) or median (interquartile range). Categorical variables such as the presence of hypertension, diabetes, hyperlipidemia, history of stroke, and occurrence of malignant brain edema are expressed as n (percentage). Fisher's exact test is used to assess differences in categorical variables, and the Kruskal-Wallis Rank Sum test is used to detect differences in continuous variables..

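### Disease-free controls and unadjusted tests mean that a patient-control marker difference cannot be attributed to stroke alone; only the descriptive differential-expression aim is affected

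*Combined protocol and SAP*

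**What the plan says.** All references are to the combined protocol and SAP.

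- **Controls.** Section 6.1 asks for "Age and gender matched" and "No organic diseases"; the second term is not defined. Under section 6.3, "healthy controls will be selected from outpatient health check-up populations". Section 5.3 sets their number at 91, half of the 182 patients.
- **Patients.** None of the exclusions in 6.2 removes hypertension, diabetes or hyperlipidemia. Section 10.5 plans to tabulate them: "Categorical variables such as the presence of hypertension, diabetes, hyperlipidemia".
- **Biology.** Section 2.2 says of KLK10 in endothelial cells that "it participates in regulating endothelial inflammation and atherosclerosis".
- **Blood draws.** In section 5.1, controls are bled once: "For healthy individuals, 10 ml of fasting elbow venous blood". For patients, "10 ml of elbow venous blood will be collected at admission and then at 24 hours and 7 days after stroke onset", with no fasting condition either way.
- **Aim and analysis.** Sections 1.1 and 5.1 set out to describe differential expression of KLK10, sTREM2 and GFAP. Section 10.1 gives a t-test or Mann-Whitney test for two groups, and 10.5 gives Fisher's exact and Kruskal-Wallis tests. None is adjusted. The multivariable models in 10.2 and 10.3 relate markers to outcomes among patients. Section 7.3, on reducing bias, is marked not applicable.

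**The concern.** The 91 controls leave the study after one draw and a baseline investigation (5.2) and have no 3-month outcome. Their only evident use is the marker contrast with patients. On the natural reading of 6.1 they are free of chronic vascular disease, while many patients may not be. If such disease shifts a marker, the groups will differ even if stroke does nothing to it. For KLK10 the protocol itself supplies a plausible route. Matching on age and gender does not remove this, and the planned tests make no allowance for it. What is at stake is the interpretation of a significant difference: it would be read most readily as a feature of stroke, when part or all of it could reflect risk factors.

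**Working it through.** **The plan's own figure.** 182 / 2 = 91 controls. This follows from the 2:1 ratio. No calculation in the documents sizes the patient-control contrast, and the derivation of 182 does not bear on this point.

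**Inputs.** From the documents: 182 patients, 91 controls, two-sided 5% tests. Assumed, because the documents give no values: no true stroke effect; hypertension in 50-70% and diabetes in 30% of patients, independent of each other; neither in controls; a marker shift of 0.2-0.4 SD for each condition.

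**Unadjusted comparison**

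- SE = sqrt(1/182 + 1/91) = 0.128 SD.
- Bias = sum over conditions of (prevalence in patients × shift).
- P(reject) = P(|Z + bias/SE| > 1.96).

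| Scenario | Bias (SD) | Rejection with no stroke effect |
|---|---|---|
| Hypertension only, 50%, 0.2 SD | 0.5 × 0.2 = 0.10 | 12% |
| Hypertension only, 70%, 0.4 SD | 0.7 × 0.4 = 0.28 | 59% |
| Adding diabetes, low end | 0.10 + 0.3 × 0.2 = 0.16 | 24% |
| Adding diabetes, high end | 0.28 + 0.3 × 0.4 = 0.40 | 88% |

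A different set of assumptions (one comorbidity in 30-70% of patients, shift 0.2-0.5 SD) gives a bias of 0.06-0.35 SD and rejection in 7.5-78%.

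**Can adjustment repair it?** Patients with neither condition are comparable with the controls on these factors. Their expected number is 182 × (1 − h) × (1 − d), where h and d are the two prevalences:

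- h = 0.5: 182 × 0.5 × 0.7 = 64.
- h = 0.7: 182 × 0.3 × 0.7 = 38.

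A regression on group, hypertension and diabetes estimates the patient-control difference at the level where both conditions are absent. That level is observed in both groups, so the estimate is unbiased under the assumed model. With independent conditions its variance, in SD² units, is 1/91 + (1/182) × [1 + h/(1 − h) + d/(1 − d)]:

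- h = 0.5: 0.01099 + (1 + 1 + 0.429)/182 = 0.0243, so SE = 0.16.
- h = 0.7: 0.01099 + (1 + 2.333 + 0.429)/182 = 0.0317, so SE = 0.18.

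Simulating the low and high scenarios that include diabetes, with no stroke effect, gave unadjusted rejection of about 23-24% and 86%. The second is slightly below the 88% above because comorbidity also adds variance among patients, which the formula ignores. Adjusted rejection was about 5% in both, as was rejection after restriction to patients with neither condition.

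**Price in precision.** The difference detectable with 80% power is (1.96 + 0.84) × SE: 0.36 SD unadjusted, and about 0.44-0.50 SD adjusted. Adding hyperlipidemia would widen this further; no rate is assumed for it here.

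**The case against.** The strongest reply is that a healthy reference group is a legitimate choice. The plan calls the controls healthy throughout, says only that differential expression will be observed, and nowhere promises to ascribe the difference to stroke. No primary or secondary endpoint uses the controls. The reading of 6.1 as excluding hypertension and diabetes is an inference, and the size of any bias is assumed. Section 2.2 ties only KLK10 to atherosclerosis; nothing in the documents says that these conditions shift sTREM2 or GFAP. Serial sampling within patients also holds chronic disease constant for the dynamic-change part of the aim.

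Most of this stands, and it limits the point without removing it: the between-group contrast is still a stated aim, and the tests given for it are unadjusted.

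A reader might infer three stronger things that the documents do not support:

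- **That adjustment is useless because no control has the conditions.** The comparison needs patients without them, and 6.2 does not keep such patients out.
- **That the prognostic findings are compromised.** Sections 9.1, 9.2, 10.2 and 10.3 concern outcomes that only patients have.
- **That fasting biases the contrast.** Patients' fasting status is not stated for any draw, the 24-hour and 7-day samples could be fasting, and nothing says that feeding alters these markers. It is a gap in recording, not a demonstrated bias.

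**Conclusion.** The point holds for the descriptive patient-control contrast only. As planned, a difference in KLK10, and possibly in sTREM2 or GFAP, cannot be attributed to stroke alone. The 24-88% false rejection shows what moderate risk-factor shifts could do; it is not an estimate for this study. It rests on the assumed prevalences and shifts, and on controls having neither hypertension nor diabetes.

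For the measured conditions the gap lies in the analysis, and adjustment closes it at a cost in precision. The adjusted result describes the difference among people without these conditions. Carrying it over to patients who have them assumes that the difference is the same there. Unmeasured differences between check-up attenders and inpatients remain.

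**What to change.** 1. **Main comparison (10.1 and 10.5).** State that each marker, transformed if needed, is regressed on group with adjustment for age, gender, hypertension, diabetes and hyperlipidemia. Name the patient time point that is compared with the single control sample.
2. **Sensitivity analysis.** Repeat the comparison using only patients without these conditions. Expect about 38-64 of 182 with neither hypertension nor diabetes on the assumed rates; excluding hyperlipidemia as well would leave fewer.
3. **Data.** State in 6.1 which conditions the control criterion excludes, and record the same risk-factor items in controls. Record fasting status or time since last meal at every draw in both groups.
4. **Conclusion.** Describe the result as AIS patients versus disease-free people, not as an effect of stroke alone.

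The cost is a paragraph of analysis text, one or two data fields, and a standard error of about 0.16-0.18 instead of 0.128 SD. The numbers recruited and the draws do not change.

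Admitting controls with hypertension or diabetes and frequency-matching on them is optional. It would recover precision and extend the comparison to patients with these conditions, but it answers a different question from a healthy reference group. It also depends on enough such attenders being available, which section 6.3 does not establish.

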6.2 Exclusion criteria

- Intracranial hemorrhage;
- Pregnancy;
- Stroke with unknown onset time;
- Malignant tumors;
- Hematologic disorders;
- Severe liver or kidney dysfunction;
- Recent myocardial infarction (less than 3 months);
- Ongoing anti-inflammatory drug treatment

6.3 Recruitment of research subjects

- Source of subjects: AIS patients will be recruited from inpatients in the Department of Neurology at the Northern Campus; healthy controls will be selected from outpatient health check-up populations who have undergone routine blood tests, biochemical tests, cranial CT, or MRI
- Recruitment site: Ruijin Hospital Northern Campus

6.4 Method of allocating research subjects

not applicable

7. Study Intervention

7.1 Administration of Study Intervention

not applicable

7.1.1 Description of study intervention

not applicable

7.1.2 Dosage and administration method

not applicable

7.1.3 Establishment, Storage, Unblinding Method, and Emergency Unblinding Procedure for the Trial Drug Code

not applicable

7.1.4 Items and frequency of clinical and laboratory examinations to be conducted

- 1) Collect reports of complete blood count and biochemical tests upon admission: including neutrophil and lymphocyte counts, blood glucose, creatinine, and high-sensitivity C-reactive protein levels.
- 2) Collect blood pressure information upon admission.
- 3) Collect reports of cranial MRI or CT scans upon admission, and record the Alberta Stroke Program Early CT Score (ASPECTS) (0-10 points).
- 4) Measure levels of neuroinflammatory markers KLK10, sTREM2, and GFAP in plasma at admission, and at 24 hours and 7 days after stroke
- 5) Assess the degree of neurological impairment using the National Institutes of Health Stroke Scale (NIHSS) at admission, and at 24 hours, 4 days, 7 days, and discharge after stroke.
- 6) Collect information on infarct volume within 7 days after stroke, measured using diffusion-weighted imaging (DWI) (J Neuroinflammation. 2020 Apr 7;17(1):107).
- 7) Collect information on brain edema grading within 7 days after stroke, measured using non-contrast cranial CT scans. The severity of brain edema in AIS patients is assessed with a score of 0-3 based on our established method (Clin Neurol Neurosurg. 2022 Nov 2;223:107507).
- 8) Collect information on hemorrhagic transformation within 7 days after stroke, measured using non-contrast cranial CT scans.
- 9) Record the Modified Rankin Scale (mRS) score at 3 months after stroke.

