7.4 Follow-up and Compliance

3 months mRS Score: 0-2 indicates a good outcome, 4-6 indicates a poor outcome
Grading Description:

- 0: No symptoms at all

- 1: No significant disability despite symptoms; able to carry out all usual duties and activities
- 2: Slight disability; unable to carry out all previous activities but able to look after own affairs without assistance
- 3: Moderate disability; requiring some help but able to walk without assistance
- 4: Severe disability; unable to walk without assistance and unable to attend to own bodily needs without assistance
- 5: Very severe disability; bedridden, incontinent, and requiring constant nursing care and attention
- 6: Death

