9.1 Primary Endpoint Evaluation

The study examines the association between plasma levels of KLK10, sTREM2, and GFAP with favorable functional outcomes at 3 months after stroke onset.

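### No pre-stroke function measure is specified and prior dependence is not an exclusion, so prior function is an unmeasured predictor and possible confounder of the primary marker-outcome association

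*Combined protocol and SAP*

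**What the plan says.** - **Outcome measurement.** The examination list in 7.1.4 has a single mRS item: "Record the Modified Rankin Scale (mRS) score at 3 months after stroke". The schedule in 7.6 marks mRS only in the follow-up period.
- **Outcome classes.** Section 7.4 states "3 months mRS Score: 0-2 indicates a good outcome, 4-6 indicates a poor outcome". Grade 3, described as "3: Moderate disability; requiring some help but able to walk without assistance", is in neither class. Section 9.1 frames the primary endpoint as association of the three markers "with favorable functional outcomes at 3 months after stroke onset".
- **Eligibility.** Section 6.1 admits "patients with first-ever acute ischemic stroke (AIS) who are hospitalized at our hospital, aged ≥ 18 years, with no restriction on gender". There is no upper age limit and no requirement of independence before the stroke. None of the eight exclusions in 6.2 concerns prior function. The requirement to be free of organic disease applies to the healthy controls only.
- **Baseline data.** The variables named in 10.5 are demographic, comorbidity, laboratory, imaging, NIHSS and marker data. No prior mRS or dependence item is among them. The schedule in 7.6 has a line for basic information whose content is not itemised.
- **Analysis.** Section 10.2 plans univariate and multivariate logistic regression without naming covariates. Section 7.3, on reducing bias, is marked as not applicable.

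**The concern.** An mRS of 0-2 requires, at worst, that the patient can manage their own affairs without help. Someone who already needed help before the stroke would not be expected to reach that grade at 3 months, whatever the stroke did and whatever the marker level was. Restricting entry to first strokes removes disability left by an earlier stroke, but not disability from other causes. NIHSS and infarct volume describe the acute event and do not stand in for prior function.

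Prior function is thus a strong predictor of the primary outcome that no named item captures. If marker levels also differ in people who were already dependent, for example through age or comorbidity, prior function confounds the primary association. Without a recorded value the analysis can neither adjust for it nor restrict on it. At stake are the size of the reported odds ratio and, for a marker with no effect, the possibility of an apparent association.

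**Working it through.** **Inputs from the protocol.** 182 AIS patients, 40% poor outcome, OR 2.0, correlation 0.5 with other factors, alpha 0.05, power 0.8 (all 5.3); two-sided tests (10.1).

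**Inputs assumed.** The protocol gives no figure for prior dependence. Assume a share f of 5% or 10%, and a marker mean d SD higher in these patients, with d = 0, 0.5 or 1.0. Read the OR of 2.0 as per SD. Count all of these patients as poor; this is the upper case, because some may end at mRS 3.

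**The plan's own figure.** For a continuous marker, n = (1.960 + 0.842)² / [0.4 × 0.6 × (ln 2)² × (1 − R²)]. This gives 69 with R² = 0, 91 with R² = 0.25 (r = 0.5) and 137 with R² = 0.5. The stated 182 is not reproduced; it is twice 91, and no doubling is explained. That is a separate matter, and this point does not depend on it.

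**Step 1: numbers affected.** Expected poor outcomes: 0.40 × 182 = 72.8.
- f = 5%: 0.05 × 182 = 9.1 patients, and 9.1 / 72.8 = 12.5% of poor outcomes.
- f = 10%: 0.10 × 182 = 18.2 patients, and 18.2 / 72.8 = 25%.

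**Step 2: model.** In previously independent patients the marker x is standard normal and P(poor | x) = expit(a + ln 2 × x). The intercept a is set so that their poor rate is (0.40 − f)/(1 − f): 0.35/0.95 = 0.368 at 5% and 0.30/0.90 = 0.333 at 10%. This keeps the overall rate at 40%. In dependent patients x has mean d and the outcome is poor with probability 1. The large-sample slope of an ordinary logistic regression of poor outcome on x, ignoring prior function, is solved numerically. For a null marker, ln 2 is replaced by 0.

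**Step 3: results.**

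| Marker shift d | True OR 2.0, f = 5% | True OR 2.0, f = 10% | Null marker, f = 5% | Null marker, f = 10% |
|---|---|---|---|---|
| 0 | 1.88 | 1.76 | 1.00 | 1.00 |
| 0.5 SD | 2.02 | 2.03 | 1.06 | 1.13 |
| 1.0 SD | 2.13 | 2.27 | 1.13 | 1.26-1.27 |

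The last cell is 1.26 per SD in independent patients, the scale of the other cells, and 1.27 per SD of the whole sample.

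**Hand check of the null columns.** The poor group's mean marker is raised by (f/0.40) × d, so OR ≈ exp[(f/0.40) × d]. At f = 5%, d = 0.5: exp(0.125 × 0.5) = 1.06. At f = 10%, d = 0.5: exp(0.25 × 0.5) = 1.13. At f = 10%, d = 1.0 the approximation gives exp(0.25) = 1.28, slightly above the exact value.

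**Step 4: sensitivity.** If the independent patients themselves have a 40% poor rate, the d = 0 results are 1.89 (5%) and 1.80 (10%), and the null-marker range is 1.06-1.23.

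**Step 5: power at 182 with d = 0.** With no dependent patients it is 0.98 (R² = 0.25) or 0.90 (R² = 0.5). At f = 5% it is 0.95 or 0.84; at f = 10%, 0.90 or 0.75.

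**The case against.** **Outcome classes.** A reader might infer that every previously dependent patient is counted as a poor outcome caused by the stroke. The protocol does not support this. Section 7.4 defines poor as 4-6, so a patient at mRS 3 before and after the stroke is in neither class. That patient is a non-event only if the analysis is 0-2 versus the rest, which 9.1 may imply but does not state. Classification as poor is to be expected only for pre-stroke mRS 4-5. The protocol nowhere attributes poor outcomes to the stroke: it sets out to predict 3-month prognosis, and dependence at 3 months is a legitimate prognostic endpoint whatever its origin. This stands, and it is why prior function is described here as an unmeasured predictor and possible confounder, not as misclassification.

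**Direction.** A reader might also infer that the gap necessarily dilutes true marker effects. It does so only when the marker is unrelated to prior dependence; with a 0.5 SD shift the bias is close to nil, and with 1.0 SD it is upward. This stands.

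**Whether it is recorded.** The basic-information line in 7.6 is not itemised and might include prior function. So the claim is that no such item is specified, not that none will be collected.

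**Size.** The shares and shifts are assumed, and the calculation is univariate. Age, comorbidity and NIHSS could absorb part of a frailty link if they enter the multivariate model, and 6.2 removes some causes of prior disability, such as malignancy and severe liver or kidney dysfunction. This limits the size but does not close the gap: 10.2 names no covariates, and none of these variables measures prior function.

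**Conclusion.** The point holds as an inexpensive improvement, not as a defect that invalidates the primary analysis. The protocol specifies no measure of prior function and does not exclude prior dependence, so the primary model cannot account for it.

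Under the assumed 5-10% prior dependence, with all such patients counted as poor, the odds ratio for a true effect of 2.0 lies anywhere from 1.76 to 2.27, depending on how the marker relates to prior dependence. A null marker can show up to about 1.27. The direction is unknown. If some of these patients end at mRS 3 and are left out of a 0-2 versus 4-6 comparison, fewer are forced into the poor class than assumed here. Power is a lesser issue: among the cases shown it falls below 0.80 only at 10% dependence with R² = 0.5.

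**What to change.** 1. Add pre-stroke mRS to 7.1.4 and the 7.6 schedule, taken by history from the patient or family at admission, and list it among the baseline variables in 10.5.
2. Name it as a covariate in the 10.2 multivariate model, entered as an ordinal score. A yes/no dependence indicator could predict poor outcome perfectly and cause separation. State in advance that penalised (Firth) logistic regression will be used if separation occurs.
3. Repeat the primary analysis in patients with pre-stroke mRS 0-2.
4. State how mRS 3 at 3 months is handled, so that 7.4 and 9.1 agree. Otherwise the place of these patients in the analysis stays undefined.

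**Cost.** One history question, one case-report field and one extra model parameter; no new procedure or staff. The value is a retrospective report with some recall error, and reconstructing it later would be less reliable. Under the assumed shares, the sensitivity analysis keeps about 182 − 9 = 173 to 182 − 18 = 164 patients.
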